9.2.3 Assessment of exploratory outcomes

Exploratory outcomes will be the severity of depressive symptoms (Beck Depression Inventory, BDI) (Beck et al., 1988), self-constructed visual analogue scales measuring mood, tiredness, concentration and subjective sleep quality, daytime sleepiness (Lapin et al., 2018), medication (self-reported) and hospitalization (self-reported number of inpatient stays within the follow-up period).

For all mentioned questionnaires, the primary metric will be the total score of the respective questionnaire. We will also perform additional analyses to compare the number of patients with response and remission between the two trial groups. Following Morin et al., response is defined as an improvement of > 7 points on the ISI (Morin et al., 2011). Remission is defined as an ISI score of < 8.

9.2.4 Assessment of safety outcomes

9.2.4.1 Adverse events

At T0, T1, T2, T3, and T4, participants will be asked about significant negative life events in order to assess possible adverse effects of the treatment. AEs will be categorized concerning the type of the reaction, severity, relatedness to the intervention, action taken, and outcome (Raisch et al., 2001).

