2.2 Categorisation of study

The psychotherapeutic protocol used in this study (Cognitive Behavioral Therapy for Insomnia) is non-invasive. Comparable therapeutic protocols have been thoroughly investigated in patients with insomnia without adverse events. Sleep restriction as used in this therapy may be associated with temporary daytime sleepiness. No long-lasting or serious adverse effects of these psychotherapies are known. In addition, multiple previous studies have shown that Cognitive Behavioral Therapy for insomnia is also feasible as an online application. The new aspect of this study is a change of the target group: instead of patients with insomnia only, the intervention will be applied in patients with insomnia and mental disorders (both disorder groups are category F in the ICD-10). We have no reason to assume that the psychotherapeutic protocol is associated with unexpected risks in this target group. The internet-based self-help program platform developed by [name], University of Bern, that will be used in this study has received a CE mark in 2018 that is valid for 5 years. All examinations and interventions in this study are in accordance with current safety standards and the risk associated with a participation in this study is regarded as minimal. Thus, this study belongs to category A.

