4.5 Safety Objectives

The study aims to assess short- and long-term safety of SleepExpert and its tolerability in terms of incidence of sleep- and mental-health related side effects and use of sleep medication.

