5.4 Safety Outcomes

At T0, T1, T2, T3, and T4, participants will be asked about significant negative life events in order to assess possible adverse effects of the treatment. AEs will be categorized concerning the type of the reaction, severity, relatedness to the intervention, action taken and outcome (Raisch, Troutman, Sather, & Fudala, 2001).

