9.3.2 Timepoints T0 to T4

Time point T0 (day 0):

- Insomnia Severity Index
- Brief Symptom Inventory
- Beck Depression Inventory
- Visual analogue scales (subjective sleep quality, mood, concentration, and tiredness)
- Sleep diary will be handed out
- medication status
- adverse events

Time point T1 (day 7±2):

- Insomnia Severity Index
- Visual analogue scales (subjective sleep quality, mood, concentration, and tiredness)
- sleep diary will be checked
- medication status
- adverse events

Time point T2 (day 14±2):

- Insomnia Severity Index
- Brief Symptom Inventory
- Beck Depression Inventory
- Visual analogue scales (subjective sleep quality, mood, concentration, and tiredness)
- sleep diary will be checked
- medication status
- adverse events

Time point T3 (day 84±7):

- Insomnia Severity Index
- Visual analogue scales (subjective sleep quality, mood, concentration, and tiredness)

- sleep diary will be checked
- medication status
- adverse events

Time point T4 (day 182±7):

- Insomnia Severity Index
- Brief Symptom Inventory
- Beck Depression Inventory
- Visual analogue scales (subjective sleep quality, mood, concentration, and tiredness)
- sleep diary will be checked
- medication status
- adverse events

For details regarding the mentioned questionnaires, please see chapter 5.

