10.3 Medical Device Category A studies

Device deficiencies and all **adverse events (AE)** including all **serious adverse events (SAE)** are collected, fully investigated, and documented in the source document and appropriate case report form (CRF) during the entire study period, i.e. from patient's informed consent until the last protocol-specific procedure. Documentation includes dates of event, treatment, resolution, assessment of seriousness, and causal relationship to device and/or study procedure [ISO 14155, 6.4.1.].

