10.3.1 Foreseeable adverse events and anticipated adverse device effects

Potential adverse events are transitional worsening of the sleep disorder and / or the mental disorder, daytime tiredness and daytime sleepiness. No SAE that could be related to the investigational device or study procedures are expected during this clinical trial.

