10.3.2 Definition and Assessment of safety related events

Adverse Event (AE):

Any untoward medical occurrence, unintended disease or injury or any untoward clinical signs (including an abnormal laboratory finding) in participants, users or other persons whether or not related to the investigational medical device [ISO 14155: 3.2].

This includes events related to the investigational device or the comparator and to the procedures involved. For users or other persons this is restricted to events related to the investigational medical device.

Adverse Device Effect (ADE):

Adverse event related to the use of an investigational medical device [ISO 14155: 3.1].

This includes any adverse event resulting from insufficient or inadequate instructions for use, deployment, implantation, installation, operation, or any malfunction of the investigational medical device. This includes any event that is a result of a use error or intentional misuse.

Serious Adverse Event (SAE) [European regulation on medical devices 2017/745, art. 58]:

Any adverse event that led to any of the following:

- (a) death,
- (b) serious deterioration in the health of the subject that resulted in any of the following:
 - (i) life-threatening illness or injury,
 - (ii) permanent impairment of a body structure or a body function,
 - (iii) hospitalisation or prolongation of patient hospitalisation,
 - (iv) medical or surgical intervention to prevent life-threatening illness or injury or permanent impairment to a body structure or a body function,
 - (v) chronic disease,
- (c) foetal distress, foetal death or a congenital physical or mental impairment or birth defect.

These are submitted to the EC via BASEC within 7 days (see below chapter 10.2.3). A planned hospitalisation for pre-existing condition, or a procedure required by the protocol, without a serious deterioration in health, is not considered to be a serious adverse event.

Device deficiency:

Inadequacy of a medical device related to its identity, quality, durability, reliability, safety or performance,

such as malfunction, misuse or use error and inadequate labelling [ISO 14155: 3.15].

Device deficiency with SAE potential:

Device deficiencies that might have led to a serious adverse event if a) suitable action had not been taken or b) intervention had not been made or c) if circumstances had been less fortunate.

Health hazards that require measures:

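### The adverse-event question asks about negative life events, not the side effects the protocol foresees, and the safety analysis counts adverse events only, so side effects would probably be under-counted

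*Combined protocol and SAP*

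**What the plan says.** The safety objective (section 4.5) covers short- and long-term safety and "tolerability in terms of incidence of sleep- and mental-health related side effects and use of sleep medication". Section 10.3.1 names what is expected: "Potential adverse events are transitional worsening of the sleep disorder and / or the mental disorder, daytime tiredness and daytime sleepiness". Section 2.2 gives a reason for the last of these: "Sleep restriction as used in this therapy may be associated with temporary daytime sleepiness".

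The stated way of finding such effects is in sections 5.4 and 9.2.4.1: at T0 to T4 "participants will be asked about significant negative life events in order to assess possible adverse effects of the treatment". Events are then sorted by type, severity, relatedness, action and outcome.

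Section 10.3.2 defines an adverse event broadly, as "Any untoward medical occurrence, unintended disease or injury or any untoward clinical signs". Section 10.3 adds a general duty that all adverse events "are collected, fully investigated, and documented in the source document and appropriate case report form (CRF) during the entire study period". Table 1 and section 9.3.2 list adverse events at T0 to T4 without saying how they are asked about.

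The safety analysis (section 11.4.4) describes adverse-event frequencies by category and compares the groups with chi-square tests.

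**The concern.** A patient who feels sleepier, more tired or more unwell while time in bed is being shortened has not had a negative life event in the ordinary sense, and may not mention it when asked about one. The prompt is therefore narrower than the protocol's own definition of an adverse event and points away from the effects it expects.

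The safety analysis is built on adverse-event counts, so what the prompt misses does not reach it. Section 3.4 says there are no clinical data on exactly this product, section 2.2 describes the target group as new, and section 11.2 makes a large confirmatory trial depend on encouraging results. A low count that partly reflects the way of asking could be carried into that trial as evidence of tolerability.

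**Working it through.** The plan gives no figure on this point, so the main check sets the sections side by side. For each effect foreseen in section 10.3.1, I looked for a scheduled measure (Table 1 in section 1.1, and section 9.3.2), its role (sections 5.1 to 5.3 and 9.2.3), and whether section 11.4.4 uses it.

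| Foreseen effect | Scheduled measure | Role | In safety analysis |
|---|---|---|---|
| Worse sleep | ISI and sleep-quality visual analogue scale (VAS), T0 to T4 | primary; exploratory | no |
| Worse mental state | BSI and BDI at T0, T2, T4; mood VAS, T0 to T4 | secondary; exploratory | no |
| Daytime tiredness | tiredness VAS, T0 to T4 | exploratory | no |
| Daytime sleepiness | none | exploratory (Epworth named in 4.4 and 11.1) | no |

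(Section 5.2 also lists the BSI at 1 and 12 weeks; the table follows Table 1 and section 9.3.2, which agree with each other.)

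Three things follow.

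1. Sleepiness is the real hole in measurement. Section 5.3 refers to Table 1 for the timing of exploratory outcomes, but Table 1 has no sleepiness row, and neither do the visit lists in 9.3.2.
2. For the other three effects the data exist, but nothing turns a worse score into a safety event. Section 9.2.3 defines ISI response (improvement of more than 7 points) and remission (score below 8), with no threshold for deterioration. The planned mixed models compare group averages, which can improve while some patients get worse.
3. Medication status is recorded at screening and T0 to T4, so use of sleep medication can be derived. Section 4.5 makes it part of the safety objective, but section 11.4.4 does not mention it.

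**Illustration of size.** Inputs, all assumed: n = 30 treated patients (section 6.1 fixes only the total of 60, so this takes an even split), true incidence p = 20%, and a share c of cases captured by the prompt. Clustering is ignored and the prompt is treated as the only route of report.

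- True cases expected: 30 × 0.20 = 6.
- Reported cases expected: 6c, which is 0.6, 1.5 and 3 for c = 10%, 25% and 50%.
- Chance of no report: (1 − p·c)^30, which is 0.98^30 = 55%, 0.95^30 = 21% and 0.90^30 = 4%.
- Upper end of the two-sided 95% interval for 0 of 30: 1 − 0.025^(1/30) = 11.6%, well below the assumed 20%.

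**Illustration for the group comparison.** Assume true rates of 50% and 20%, 30 per arm, two-sided 5%, and equal capture in both arms. With p̄ the mean of the two captured rates, power = Φ{[|p1 − p0| − 1.96·√(2p̄(1−p̄)/n)] / √([p1(1−p1) + p0(1−p0)]/n)}.

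- Full capture (50% v 20%): (0.300 − 0.241)/0.117 = 0.50, power 0.69.
- Half captured (25% v 10%): (0.150 − 0.192)/0.096 = −0.44, power 0.33.
- A quarter captured (12.5% v 5%): (0.075 − 0.143)/0.072 = −0.94, power 0.17.

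**The case against.** A reader might infer that the foreseen effects are not asked about at all and that the safety objective cannot be answered. The documents do not support either inference. Sleep, mental state and tiredness are self-reported on scheduled scales in both arms, and medication status is recorded throughout. Worsening could be derived from these data; what is missing is a definition and a planned analysis.

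It is also fair to say that section 10.3 obliges the team to record every adverse event, that patients see clinical staff daily while on the ward (section 8.1.1), and that sorting events by type of reaction and relatedness suggests something broader than life events was intended. The CRF is not among the documents, so the exact question put to patients is unknown. All of this stands, and it makes the loss smaller than a single-channel calculation suggests. It does not close the gap: section 10.3 states a duty without a way of asking, daily ward contact ends at discharge (typically after one to eight weeks) while follow-up runs to week 26, and no scheduled instrument covers sleepiness.

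Finally, this is a category A pilot, described in section 11.2 as mainly for qualitative experience and preliminary efficacy. That limits the weight of the point, but section 4.5 still sets a safety objective in terms of incidence.

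**Conclusion.** The point holds as a mismatch between the prompt, the foreseen effects and the safety analysis. The only stated adverse-event question does not target the effects in section 10.3.1 or the objective in section 4.5. Three of the four effects are measured, but outside the safety analysis; daytime sleepiness is measured at no visit. Followed as written, the plan would probably under-count side effects.

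The direction rests on the wording of the plan and on the judgement that patients rarely regard sleepiness or a temporary setback as a life event. The size is unknown. The 55% to 4% range for no reports, and the fall in power from 0.69 to 0.17, are correct arithmetic on assumed incidence, capture and group size, and the documents give none of these apart from the total of 60. Nor do they say that a zero count would be read as an 11.6% ceiling. This is a cheap improvement to make before recruitment, not a flaw that invalidates the trial.

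**What to change.** - **Sections 5.4 and 9.2.4.1:** at T0 to T4, in both arms and with the same wording, ask an open adverse-event question plus a fixed checklist of the four effects in section 10.3.1, with severity and onset. Count only effects that are new or worse than at T0. The T0 record is essential because poor sleep and mental symptoms are already present at entry.
- **Table 1 and section 9.3.2:** add the Epworth scale, which sections 4.4 and 11.1 already name.
- **Section 11.4.4:** report per arm the number of patients worse than T0 by a margin fixed in advance on the ISI, BSI, BDI and tiredness VAS, and the use of sleep medication from the medication status already recorded. Without a margin, a one-point fluctuation would count as a safety signal.

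The cost is a few minutes per visit and more minor events to record and classify. The score-worsening and medication tables use data already scheduled.

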9.2.4.2 Laboratory parameters

Not applicable. No laboratory parameters will be assessed in this study.

9.2.4.3 Vital signs

Not applicable. No vital signs will be assessed in this study.

9.2.5 Assessments in participants who prematurely stop the study

For participants who discontinue the study intervention but do not withdraw from participation in the study, study visits and data collection will continue in the same way as for non-withdrawn participants.

Dropouts before start of treatment (i.e. non-starters) will be replaced by recruitment of new participants.

Patients who started the intervention but who were prematurely withdrawn from the study will not be replaced by newly enrolled patients.

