6. STUDY DESIGN

6.1 General study design and justification of design

This project is a prospective randomized controlled clinical pilot trial with a cluster-crossover design

involving two groups: An interventional group (TAU, plus SleepExpert) and a control group (TAU plus sleep monitoring).

Two different wards in the trial site (UPD Bern) will constitute the clusters. The study is conceptualized with a crossover, i.e. clusters (wards) will first be randomized to one of the groups for a duration of 4 months. After a washout-phase of two months, they will then be allocated to the other group for another 4 months. The order (TAU plus SleepExpert first vs. TAU plus sleep monitoring first) will be randomly allocated in a 1:1 fashion.

A total of 60 patients will be included. Patients will be assessed before the intervention (T0) and at the following time-points after the start of the intervention: 1 week (T1), 2 weeks (T2), 12 weeks (T3) and 26 weeks (T4).

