6.2.3 Other methods of minimising bias

- The primary applicant is a staff member at the sleep clinic of the University Psychiatric Services Bern. The resources at this established, specialized sleep clinic will ensure that included patients are carefully diagnosed, i.e. that only patients fulfilling the defined eligibility criteria will be included. This ensures generalizability of the results to the intended population.
- Study attrition and reasons for dropout will be carefully documented throughout the study period.
- An intention to treat analysis will be provided since a per-protocol analysis may result in biased effects if many patients drop out due to (perceived) inefficacy.
- The outcome measures are widely used, valid, and reliable measures that have been recommended by experts for the research assessment of insomnia (Buysse, Ancoli-Israel, Edinger, Lichstein, & Morin, 2006).
- Therapists will be experienced, well-trained, and supervised.
- The trial will be registered in a publicly accessible database before recruitment of the first subject. Hypotheses and the analysis plan will be made publicly available. This precludes that the analysis plan is changed after inspection of the data ("fishing for significances").

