7.4 Criteria for withdrawal / discontinuation of participants

Participants will be withdrawn from the study immediately if there are any concerns about the participants' safety. Participants can also choose to withdraw from the study at any time, and are not required to provide their reason for withdrawing from the study. Coded data acquired before withdrawal will be analyzed.

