8. STUDY INTERVENTION

8.1 Identity of Investigational Products (treatment / medical device)

8.1.1 Experimental Intervention (treatment / medical device)

General information

Both groups will receive psychiatric inpatient treatment-as-usual (TAU). TAU will be provided according to current treatment guidelines for the respective mental disorders. Within the trial period, TAU will be delivered as usual in the respective hospitals. No restrictions with regard to pharmacotherapy, psychotherapy, or any other inpatient therapy or subsequent outpatient care will result from participation in the SleepExpert trial.

TAU will consist of the following interventions: daily visit by a physician or psychologist, if necessary individualized pharmacological treatment according to current guidelines, individualized disorder-specific psychotherapy according to current guidelines, daily contact with a psychiatric nurse, ergo therapy, and other group therapies according to a personalized schedule (e.g. music therapy, art therapy, relaxation therapy, etc.). The duration of the inpatient stay will be adapted to the progress of the individual patient and will vary from participant to participant. The duration of the stay is typically between one to eight weeks, exceptions are possible.

The TAU plus SleepExpert group will receive a specific treatment for insomnia. This treatment will consist of the following three phases:

- 1) a face-to-face treatment initiation guided by a medical doctor/ psychologist in a group format (1 hour),
- 2) self-managed implementation of behavioral changes assisted by an online application ("Become your own SleepExpert") and coached by nurses (two individual contacts per week of about 5 min duration), and
- 3) self-management by the patients assisted by the same online application after discharge from the hospital.

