8.1.2 Control Intervention (standard/routine/comparator treatment / medical device)

Patients in the control group will receive the same TAU as the experimental group (see 8.1.1).

In addition, patients in the control group (TAU plus sleep monitoring) receive a smartphone app (sleep monitoring). No further interventions will be provided through this app.

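### Non-starters are replaced after the ward-period has fixed the arm, and the start of treatment is undefined and differs by arm, so the rule may select patients differently in the two arms

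*Combined protocol and SAP*

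**What the plan says.** Section 9.2.5, repeated in 11.5: "Dropouts before start of treatment (i.e. non-starters) will be replaced by recruitment of new participants". Section 9.2.5 adds: "Patients who started the intervention but who were prematurely withdrawn from the study will not be replaced by newly enrolled patients". Whether a patient has started therefore decides whether he or she is replaced, yet no section defines the start for either arm.

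The arm is set at ward level before any patient is recruited: "clusters (wards) will first be randomized to one of the groups for a duration of 4 months" (6.1; also 7.3).

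The first treatment step differs by arm. In SleepExpert it is "a face-to-face treatment initiation guided by a medical doctor/ psychologist in a group format (1 hour" (8.1.1). Control patients "receive a smartphone app (sleep monitoring" (8.1.2), and section 3.6 describes monitoring as daily diary entries in that app.

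On the analysis set, 6.2.3 says: "An intention to treat analysis will be provided since a per-protocol analysis may result in biased effects". Section 11.4.1 instead puts all analyses on an as-treated basis. Section 7.4 says: "Coded data acquired before withdrawal will be analyzed". Sections 8.5 and 9.2.5 continue visits for patients who discontinue the intervention without leaving the study. Neither mentions patients who never began it.

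**The concern.** Replacing patients on the basis of something that happens after allocation is selection after allocation. If failing to start is more common in one arm, or is linked to prognosis differently in the two arms, the patients analysed are no longer comparable. Baseline ISI, the only patient covariate in the primary model, does not capture motivation, early discharge or deterioration.

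Patients and care providers are unblinded, and the two arms receive different information sheets (6.2.2, 7.2), so not starting can depend on the arm. The pilot is meant to inform a decision on a confirmatory trial (11.2). A contrast between patients who attended a session and patients who received an app is weaker evidence for that decision than a contrast between everyone enrolled in each arm.

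**Working it through.** **1. Order of events.** The ward-period fixes the arm (6.1, 7.3). The patient is screened, consents and completes T0, and then takes part in the intervention (9.1). Not starting falls after allocation and, for those who complete T0, after baseline.

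**2. What happens to a non-starter.** Sections 5.1 and 6.1 time T1-T4 from the start of the intervention, so a non-starter has no defined visit clock. Section 11.4.2 models the four follow-up ISI scores, so a patient with no follow-up contributes no observed outcome. Section 11.4.1 is as-treated. Section 11.5 mentions multiple imputation but does not say whether a replaced patient still belongs to the sample. Together these point to removal from the analysis, although no sentence says so.

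**3. The plan's own figure.** The concern rests on no stated figure; d = 0.65 serves only as a yardstick. Section 11.2 gives N = 60 for d = 0.65, two-sided alpha 0.05 and power 0.80. With 30 per arm (assumed), a two-sided two-sample t test has power 0.697, and 80% power needs 78 patients (76 by the normal approximation). N = 60 matches a one-sided 0.05 test (power 0.800). That mismatch is a separate matter.

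**4. Size of the selection effect.** Let p1 and p0 be the non-starter shares in SleepExpert and control. Let D be the gap in prognosis between would-be non-starters and starters, in SD units, positive if non-starters do worse, and excluding any treatment effect. If all enrolled patients have mean μ on the ISI, starters alone have mean μ − pD. With the same D in both arms, analysing starters only shifts the contrast towards SleepExpert by

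bias = (p1 − p0) × D.

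The documents give none of these inputs, so every value below is an assumption. The type I error is for a nominal 5% two-sided t test with 58 df and noncentrality bias × √(30 × 30/60) = bias × √15. It treats patients as independent and ignores ward clustering.

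| p1 | p0 | D (SD) | Bias (SD) | Share of 0.65 | Type I error |
|---|---|---|---|---|---|
| 5% | 5% | any | 0 | 0% | 5.0% |
| 10% | 0% | 0.5 | 0.10 × 0.5 = 0.05 | 8% | 5.4% |
| 10% | 0% | 0.8 | 0.10 × 0.8 = 0.08 | 12% | 6.1% |
| 20% | 5% | 0.5 | 0.15 × 0.5 = 0.075 | 12% | 5.9% |
| 20% | 0% | 0.5 | 0.20 × 0.5 = 0.10 | 15% | 6.7% |
| 30% | 0% | 0.8 | 0.30 × 0.8 = 0.24 | 37% | 15.0% |

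If D is negative the sign reverses: p1 = 20%, p0 = 0 and D = −0.5 gives −0.10 SD, against SleepExpert.

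**5. Effect of keeping non-starters.** If a share q of the SleepExpert arm gains no benefit, the effect becomes 0.65 × (1 − q): 0.585 at 10%, 0.52 at 20%, 0.455 at 30%. Two-sided power at N = 60 falls from 0.697 to 0.606, 0.508 and 0.410.

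**The case against.** The case for leaving the text alone has several parts. The sentence is a recruitment rule and orders no data to be dropped; 6.2.3, 7.4 and 8.5 can be read as keeping whatever non-starters contributed. It applies to both arms, and a control patient who never makes a diary entry could also be a non-starter. No wait for the group session is documented: T0 is day 0 and T1 is day 7±2, which places T0 and the start close together. Screening already requires that patients can take part in the group session and handle the application (3.8), and 7.1 excludes those unable to participate, both without distinction by arm. A patient who misses the session but stays in the study may not count as a dropout at all.

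Most of this stands, and it limits the claim. A reader might infer that the rule strips unmotivated or very ill patients from SleepExpert alone and so favours it. The documents do not support that. The wording is arm-neutral, and screening narrows the route for very ill patients. The sign also depends on who fails to start: unmotivated or deteriorating patients would tilt the result towards SleepExpert, whereas quickly discharged patients (stays typically begin at one week, 8.1.1) may do better, and removing them could work the other way. A reader might also infer that non-starters will go unreported, but 6.2.3 commits to documenting attrition and reasons for dropout.

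The objection does not supply a definition of start, a visit schedule for non-starters, or a statement that they are analysed. Sections 6.2.3 and 11.4.1 cannot both govern the analysis set.

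**Conclusion.** The concern holds in a limited form. The replacement rule acts after allocation, at a point that is undefined and differs by arm, and following the plan as written would most naturally remove non-starters from the analysis. Selection may therefore differ by arm. A larger loss from SleepExpert is the more likely pattern, because its first step asks more of the patient, but the direction of any bias is uncertain.

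The size cannot be derived from the documents. For p1 of 5-30%, p0 of 0-5% and D of 0.25-0.8 SD, the bias is about 0 to 0.24 SD (0-37% of d = 0.65), with type I error of 5% to 15%. At 10% or fewer non-starters it is at most 0.08 SD, with type I error 6.1%. These ranges take D as positive and equal in the two arms. Confidence is high in the mechanism and no more than moderate in the direction. The change is worth making because it costs little and removes the selection route whichever way it runs.

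**What to change.** In 9.2.5, 11.4.1 and 11.5, and in the separate SAP announced in 11.4:

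- Set one analysis entry point for both arms: consent given and T0 completed.
- Keep every such patient in the arm the ward was allocated to, whether or not treatment started.
- Time T1-T4 from T0 for non-starters, and continue those visits unless consent is withdrawn.
- Allow recruitment to be topped up by adding patients, not by substituting them for non-starters.
- Report non-starters by arm and ward-period.
- Reconcile 6.2.3, 9.2.5, 11.4.1 and 11.5 so that they name the same analysis set.

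The cost is protocol and SAP wording plus four follow-up contacts for each non-starter. Some of those visits will be missing. The estimated effect is diluted as in step 5 of the working, for example to about 0.585 at 10% or 0.52 at 20% non-starters in SleepExpert if they gain nothing. That diluted effect is what the intention-to-treat promise in 6.2.3 refers to. Topping up can recover some of the power: reaching 30 starters takes 30/0.9 = 33.3, so 34 enrolled in that arm at 10%, or 30/0.8 = 37.5, so 38 at 20%.
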